6.4 Point of enrolment

A subject is considered enrolled in the investigation at the time of consent. Prior to any clinical investigation-related procedures are undertaken, the subject signs and dates the informed consent form. The expected duration for each subject is described in section 5.10.

6.5 Subject Screening and randomization Failures

Subjects that have signed the informed consent form but fail to comply with the eligibility criteria are considered screening failures. A screening failure will be replaced by a new subject if the new subject can complete the investigation within timelines (before last subject last visit and within visit windows).

Screen failures are also considered subjects who have consented but withdraw consent prior to being randomized.

In rare cases, randomization errors can occur, and subjects are randomized by mistake, e.g., if the investigator realizes that the subject is not eligible after the subject has been randomized. In these cases, if the subject has not started study treatment and has no data registered on endpoints; the subject can be replaced by a new subject if the new subject can complete the investigation within timelines (before last subject last visit and within visit windows).

If a subject is randomized to one test sequence but by mistake gets products for the opposite sequence it will be regarded as a randomization failure. As this is an exploratory investigation the statistical analyses will in that case be based on the actual test sequence and not the randomized sequence

6.6 Subject withdrawal criteria

The subject is allowed to withdraw from the investigation at any time for whatever reason without any consequences for their future treatment outside the clinical investigation. The Investigator may withdraw a subject from the investigation at any time if they judge it to be the subject's interest.

The investigator must withdraw a subject from the investigation due to:

- Noncompliance with the CIP impacting the scientific integrity of the investigation.
- If subject's safety and wellbeing is compromised by further participation.
- Subjects lost to follow-up. At least three documented attempts will be made to verify subjects lost to follow-up. If, after these attempts are made, and there is still no response, the subject will be withdrawn from the clinical investigation

6.7 Subject Identification and Confidentiality

Subjects will be identified on the electronic CRF (e-CRF) and any other document transmitted to the sponsor by the principal investigator or clinical site staff, by a unique identification number.

Data entered on the e-CRF are confidential and will only be available to the sponsor (including sponsor delegates), members of data management teams, the statistician, data monitoring board members or clinical event committee members if involved, members of the EC or IRB and if requested to regulatory authorities.

The principal investigator for each clinical investigation site will maintain as part of the investigational file a list identifying all subjects entered into the clinical investigation.

7. Procedures

7.0. Clinical investigation-related procedures

Before initiation of the clinical investigation, Coloplast must be provided with key personnel signed and dated curricula vitae (not more than two years old) to verify qualifications. Key site personnel are those, who treat or evaluate subject data in the clinical investigation. Coloplast will ensure that all site personnel are trained in the investigation procedures, completion of the eCRFs, procedure for reporting a device deficiency, an adverse event or serious adverse event (how, when, to whom), and who to contact in case of emergency related to the investigational products.

See section 7.3 for an overview of the clinical investigation-related procedures during subject visits, telephone visits, and at each bag change.

7.1. Subject Visits

Visit 0 - Screening (Day 0)

If a potential subject is interested in participating after the first contact, a visit (visit 0) will be arranged. When arranging the visit, it will be ensured, that the subject has received the Subject Information Form and given

plenty of time to review it. The subject will receive both written and verbal information to ensure that the subject understands what was read and explained and can freely agree to participate in the investigation. The subject will, beforehand, also be informed about the possibility of bringing a companion to any subsequent visits. During the visit, the Principal Investigator or designee will provide oral information about the investigation based on the Subject Information Form. The subject has the right to wait before deciding on participation.

Visit 1 – Inclusion (Day 1)

If/when subjects decide to participate, they will be asked to sign the Informed Consent Signature Form. If a subject so desires, and it is certain that it is understood what the investigation entails, and the informed consent form has been signed, the subject is considered enrolled in the investigation. Enrolled subjects are entered in the electronic data capture system and will be randomised to either the test product or comparator. If a subject is enrolled and does not meet inclusion/exclusion criteria, they will be deemed screen failures and will not be randomized.

Once the subject has consented, the investigator and/or delegated site personnel will conduct the following:

- The investigator/study nurse will re-review study procedures.
- Subject is allocated a subject number
- Verification of inclusion/exclusion criteria
- Randomization (including subject number & name/type of randomized product)
- Collection of baseline data
 - Demographics (age, gender, height, and weight)
 - Current product (flat/concave, bag size, item numbers)
 - Stoma (age, type, cause, size, shape)
 - Bristol scale score (Appendix 1)
 - Output frequency
- Shipment of investigational products to subject

Visit 2 – Start of first test period (Day 3 + 2 days)

- Study Personnel will review App with subject and collect safety data, if applicable.
- First application of investigational product – test product OR comparator (Day 1 of Test period 1)

Test period 1:

- Testing test product / comparator product for 21 ± 2 days
- Telephone Visit at Day 7 ± 1 after application of product/comparator:
 - Investigator/study nurse must call the subject to ensure that the subject is compliant with:
 - Study procedures and
 - Completion of subject diary
- Diary completion at every bag change
- Adverse Events, if applicable
- Device Deficiencies, if applicable
- Protocol Deviations, if applicable

Visit 3 - Cross-over Visit (Day 25 ± 2 days)

- Subject will be contacted by investigator/study nurse to review procedure for cross-over
- Study Personnel will review compliance with subject and collect safety data, if applicable. Application of investigational product - test product OR comparator (Day 1 of Test period 2)
- Adverse Events, if applicable
- Device Deficiencies, if applicable
- Protocol Deviations, if applicable

Test period 2:

- Testing test product / comparator product for 21 ± 2 days
- Telephone Visit at Day 7 ± 1 after application of product/comparator:
 - Investigator/study nurse must call the subject to ensure that the subject is compliant with:
 - Study procedures and
 - Completion of subject diary
- Diary completion at every bag change
- Adverse Events, if applicable
- Device Deficiencies, if applicable
- Protocol Deviations, if applicable

Visit 4 – Completion/Termination (Day 46 ± 2 days)

- Subject will be contacted by investigator/study nurse for study completion or termination
- Study Personnel will review compliance with subject and collect safety data, if applicable.

NOTE:

1. See Appendix 2 for details on the subject questions included in the subject diary. The subject diary will be provided to the subjects using an app installed on their smart phones.
2. Subjects who are unable to complete a test period may move forward to the next visit and test period instead of dropping out of the investigation.

7.2. Safety Follow up:

Adverse events and device deficiencies will be assessed at all visits, planned and unplanned. Subjects are followed through termination of the investigation (Visit 4). Any ongoing ADEs or SADEs at study termination will be followed until resolution. All subjects are encouraged to contact the Principal Investigator, or designee, if they experience problems that they believe are related to their investigational product or participation. This is to ensure that any device-related events are documented and to safeguard the subjects' health.

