5.8. Randomisation Procedure

All subjects that meet the inclusion and exclusion criteria will be randomised to one of two treatment sequences. Both sequences examine the investigational product and the comparator investigational product. The two sequences are:

- First sequence: The investigational product, then the comparator investigational products.

- Second sequence: The comparator investigational product, then the investigational product.

Randomization will be centralized using [REDACTED]

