10.0. Statistical design, method, and analytical procedures

The primary objective will be evaluated by analysis of the primary endpoint [REDACTED]

[REDACTED]. The secondary objective will be evaluated by analysis of the secondary endpoints.

All baseline measurements, endpoints and assessments will be summarized by descriptive statistics and/or listed. Endpoints and assessments will be summarized by product. Descriptive statistics for continuous variables are presented with N, Mean, SD (standard deviation), Median, Min and Max, where N denotes the number of subjects contributing with non-missing data. For discrete variables, descriptive statistics are presented with N and percentage, where percentage is based on the total number of subjects/observations with non-missing data.

Other summaries can be made, if relevant. As it is an exploratory study no adjustment for multiple testing will be applied.

All statistical analysis and summaries will be performed with SAS (version 9.4/Enterprise Guide version 7.1)

Definition of analysis populations

Intention to Treat (ITT) and Safety populations will be defined at a formal data review meeting before database lock. As a minimum, the data manager, the clinical manager, and the statistician will be involved in the classification of subjects.

The ITT population (full analysis set) will be constituted by all included subjects with valid informed consent who have been exposed to at least one product, with information on at least one product with respect to the primary endpoint or the secondary endpoints.

Any exclusion of subjects from the ITT population must be documented. Invalid individual data points may be omitted from analysis even though the corresponding subject is part of the ITT population. Any exclusion of data points will be documented.

The Safety population will be constituted by subjects who have given informed consent.

All statistical analysis will be based upon the ITT population whereas adverse events and device deficiencies will be assessed based on the safety population.

Considering the data obtained it might be considered to make additional explorative analyses based on a subset of the ITT population.

Analysis of the primary endpoint

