10.1. Sample size

The primary objective is to investigate the performance of a new 2p coupling in comparison with the SenSura Mio Click coupling with regards to leakage at the coupling during wear in a clinical setting. This will be done by testing if the odds ratio for the estimated proportions of leakage with the two products is equal to one.

[REDACTED]

[REDACTED]

[REDACTED]

[REDACTED]

Drop-out subjects will not be replaced but to account for an assumed drop-out rate of 20%, 50 subjects will be randomized in the study.

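### Randomising at Visit 1, 2 to 4 days before the app review and first application, lets an early withdrawal use up one of the 50 unreplaced places; drawing at Visit 2 is a cheap, optional improvement

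*Combined protocol and SAP*

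**What the plan says.** **Timing.** Section 7.1 and Table 1 (section 7.3) put consent, the eligibility check, randomisation, baseline data and product shipment at Visit 1, Day 1: "Enrolled subjects are entered in the electronic data capture system and will be randomised to either the test product or comparator". Visit 2 falls on Day 3 with a window of plus 2 days. There "Study Personnel will review App with subject and collect safety data, if applicable", and the subject applies the first product.

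**Numbers.** Section 6 requires 40 subjects with the primary endpoint measured in both periods. Section 10.1 states: "Drop-out subjects will not be replaced but to account for an assumed drop-out rate of 20%, 50 subjects will be randomized in the study".

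**Replacement.** Section 6.5 allows screen failures to be replaced if timelines permit, and includes early withdrawals among them: "Screen failures are also considered subjects who have consented but withdraw consent prior to being randomized". After randomisation, it allows replacement only of subjects randomised by mistake who have started no study treatment and have no endpoint data.

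**Analysis set.** The ITT population in section 10.0 is limited to subjects "who have been exposed to at least one product, with information on at least one product" for the primary or secondary endpoints.

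**Supply.** Section 5.8 says of the two sequences: "Both sequences examine the investigational product and the comparator investigational product". Table 1 shows a single shipment, at Visit 1.

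**The concern.** The same withdrawal is handled differently depending only on whether the draw has been made. Before it, the subject is a screen failure and can be replaced. After it, the subject is a drop-out who keeps one of the 50 places, is never exposed, falls outside the ITT set and cannot count towards the 40.

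The gap also contains a practical hurdle. Leakage is recorded in an app on the subject's own smartphone, all visits are remote, and the app is first reviewed after randomisation. No inclusion criterion mentions a suitable phone. The paper diary in section 11.0 is a fallback for the app being unavailable before the study's first subject, not for one subject's failed set-up.

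The inflation from 40 to 50 leaves no reserve beyond the expected loss, so single subjects matter. What is at stake is the chance of reaching the planned number of completers. The validity of the comparison is not in question.

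**Working it through.** **Inputs from the documents**
- Randomisation: Day 1 (section 7.1, Visit 1).
- App review and first application: Day 3 to Day 5 (section 7.1, Visit 2).
- Last visit: Day 46 (section 7.1, Visit 4).
- 50 randomised, 20% drop-out, drop-outs not replaced (section 10.1).
- 40 completers required (section 6).

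**Assumed**
- Subjects drop out independently.
- The share of loss falling in the gap is not given, so a range is used.

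**1. Length of the gap.** 3 − 1 = 2 days to 5 − 1 = 4 days.

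**2. The plan's own figure.** 40 / (1 − 0.20) = 50, which reproduces. Expected completers are 50 × 0.80 = 40.0. With X ~ Bin(50, 0.80), P(X ≥ 40) = 0.584. This already includes any gap loss that forms part of the 20%.

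**3. Gap losses inside the 20%, draw moved to Visit 2.** Let q be the proportion of randomised subjects now lost in the gap. Among those who start, the completion probability is 0.80 / (1 − q). With 50 subjects randomised at Visit 2, X ~ Bin(50, 0.80 / (1 − q)):

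| q | Completion probability | Expected completers | P(at least 40) |
|---|---|---|---|
| 0 | 0.800 | 40.0 | 0.584 |
| 0.01 | 0.808 | 40.4 | 0.640 |
| 0.02 | 0.816 | 40.8 | 0.695 |

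**4. A plausibility check on q.** If the 20% were spread evenly over 46 days, the gap would take 2/46 × 20 = 0.9 to 4/46 × 20 = 1.7 percentage points. The formula in step 3 then gives P(at least 40) = 0.63 to 0.68. Even spread is itself an assumption.

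**5. Gap losses on top of 20% among starters, present timing.** With k subjects lost in the gap, X ~ Bin(50 − k, 0.80):

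| k | Expected completers | P(at least 40) |
|---|---|---|
| 0 | 40.0 | 0.584 |
| 1 | 39.2 | 0.472 |
| 2 | 38.4 | 0.358 |
| 3 | 37.6 | 0.251 |

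If the draw is made at Visit 2, the k = 0 row applies whatever the number lost earlier.

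**The case against.** **The loss is already budgeted.** The 20% is applied to all 50 randomised, so it covers anyone lost before Visit 2. This stands. A reader might infer that any gap loss lowers the chance of reaching 40 below what was planned. The documents do not support that: the chance falls below 0.58 only if total loss exceeds 20%, and nothing in them suggests it will.

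**Not everyone lost in the gap is irreplaceable.** Section 6.5 covers subjects randomised by mistake, and its example is introduced as one instance only. Inclusion criterion 3 requires subjects to do the assessments themselves, so a subject who cannot run the app may arguably be ineligible and replaceable. This stands in part: an ordinary withdrawal or lost contact is still not clearly covered.

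**The gap is short.** One could assume that 4 or 6 of the 20 points fall in it, which by the formula in step 3 gives P(at least 40) of 0.80 or 0.88. For 2 to 4 days before any product is worn, the documents offer no basis for shares that large.

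**Baseline data.** Because section 7.1 lists randomisation before baseline data, a reader might infer that knowledge of the sequence could colour baseline recording. The documents do not support this as a route to bias. Eligibility, which covers stoma type, Bristol score and current product, is verified before the draw, and the primary model has no baseline covariate.

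**The consequence is unquantified.** The basis for the 40 is redacted in section 10.1, so the power lost at 39 or 38 completers cannot be computed. This stands.

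**Cost of moving the draw.** Subjects would hold both products and be told remotely which to open, which might increase wrong-sequence use. Much of that risk exists already, since Table 1 shows one shipment for both periods and section 4.3 identifies products by name or code and lot, with no mention of period. The randomisation system is redacted, however, so a link between allocation and shipment cannot be excluded.

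**Conclusion.** The point holds as a modest, optional improvement. A subject lost between Visit 1 and Visit 2 who was not randomised by mistake takes an unreplaced place and contributes no leakage data. The sample size arithmetic is correct on its own terms, at 40 expected completers and P(at least 40) = 0.58.

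Moving the draw means the 20% allowance is spent only on subjects who start. If 1 to 2 of the 20 points fall in the gap, the probability rises to 0.640 to 0.695. If gap losses instead come on top of 20%, moving the draw keeps the planned 0.584, where the present timing gives 0.472 after one such loss. With no gap loss there is no difference.

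These figures rest on independent drop-out and an assumed gap-loss rate.

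**What to change.** **Preferred.** In section 7.1, Table 1 and the synopsis, keep consent, eligibility, baseline data and the single shipment of both products at Visit 1. Move randomisation to the Visit 2 call, after the app has been shown to work and immediately before first application. The synopsis item recording the randomised product moves with it. Section 6.5 should say that a subject who loses contact or cannot set up the app before the draw also counts as a screen failure, since it now names only ineligibility and withdrawn consent.

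**If allocation is tied to shipment.** Leave the draw at Visit 1 and extend the section 6.5 replacement rule to any randomised subject who has started no study product and has no endpoint data. Report the number of such subjects by sequence, with reasons.

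**Cost.** Wording, one row of Table 1 and, for the preferred option, one step in the electronic data capture system. The number randomised stays at 50. A few more subjects may be consented, and staff must tell each subject on the Visit 2 call which product to open first. Under the alternative, the total randomised may slightly exceed 50 and section 10.1 should say so.

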7.3. Schedule of Assessments

Table 1- Study assessments.

	PERFORMED BY	VISIT 1	VISIT 2	VISIT 3	VISIT 4
Informed consent (Allocation of Subject Number in EDC)	Investigator/Delegated Site Personnel	X			
Inclusion/Exclusion criteria	Investigator/Delegated Site Personnel	X			
Shipment of investigational products	Investigator/Delegated Site Personnel	X			
Randomization	Investigator/Delegated Site Personnel	X			
Baseline Data Collected	Investigator/Delegated Site Personnel	X			
Application of device (test product or comparator)	Subject		X	X	
Questionnaire completed at each bag change during test period 1 & 2	Subject		X	X	
Final evaluation questionnaire completed at end of study					X
Ensure Compliance	Investigator/Delegated Site Personnel		X	X	X
Telephone Call	Investigator/Delegated Site Personnel		(Day 7 of test period 1)	(Day 7 of test period 2)	
Protocol Deviations, If applicable	Investigator/Delegated Site Personnel	X	X	X	X
Adverse Events, if applicable	Investigator/Delegated Site Personnel	X	X	X	X
Device Deficiency, if applicable	Investigator/Delegated Site Personnel		X	X	X

7.4. Case Report Forms

All assessments and observations throughout the investigation for each subject must be carefully recorded in an electronic CRF (eCRF).

CRFs will be filled in by the investigator and/or delegated site personal, who have signed the Site Personnel Signature and Delegation List and Clinical Investigation Training Log. Delegated site personal will be required to complete e-learning prior to system access. Delegated personal will receive credentials.

Subjects will be asked to complete a questionnaire at every bag change. The questionnaire will be completed on a clinical trial app which will be downloaded onto their smart phones.

It is the responsibility of the Investigator that all data are entered promptly and correctly.

8. Risk – benefit analysis and ethical considerations

8.0. Risk-benefit analysis of the investigational device

This clinical study is performed to confirm that the new coupling is on par with SenSura click with regards to leakage at the coupling.

A risk analysis according to ISO 14971 Application of risk management to medical devices has been conducted. Risks have been proven minimized or eliminated through appropriate design control, confirmed by pre-clinical bench, and laboratory testing.

The risk management process has been performed in accordance with the requirements stated in ISO 14971:2012 and in accordance with internal Coloplast procedures, including design verification, validated test methods, risk analysis and completion of a biological evaluation report for the test product.

To mitigate and reduce the risks, the site personnel will be trained, according to the IFU.

The investigation is conducted in accordance with current applicable standards. Please refer to section 15.0, Statement of compliance. The rights, safety and well-being of human subjects shall prevail over the interest of science.

Risks have been proven minimized or eliminated through appropriate design control, confirmed by pre-clinical bench, and laboratory studies.

8.1. Risk-benefit for subjects participating in the clinical investigation

The investigation is conducted in accordance with current law and applicable standards, see section 15. Statement of Compliance. The rights, safety and well-being of human subjects shall prevail over the interest of science of society.

The participating subjects will contribute with important information for the development of a new coupling. Due to the actions taken to mitigate any risks, the risks and disadvantages when participating in this clinical investigation are estimated as low. The subject's health will not benefit directly from this investigation.

